### 5.4.2 Categorical Data

Categorical data will be described by summary tables of counts and percentages. This includes zero counts of all possible but unobserved categories, if any.

### 5.4.3 Continuous Longitudinal Data

Continuous data will be described by summary tables of sample characteristics by visit and for changes from baseline for visits as defined in Section 3.2.2 above. Primary and secondary continuous endpoints will be visualized by box plots by treatment group and visit.

#### Mixed Model of Repeated Measures (MMRM)

Comparisons will be done using an MMRM model including treatment, visit, treatment-by-visit interaction, as factors, and menopausal status at baseline, ICIQ-UI-SF score at baseline, and the baseline value of the respective endpoint as covariates.

The statistical model is

$$\text{Endpoint} = \beta_0 + \beta_1 \text{Otreatment} + \beta_2 \text{OVisit} + \beta_3 \text{OTreatment-by-visit} + \beta_4 \text{Omenopausal status} + \beta_5 \text{OICIQ-UI-SF score} + \beta_6 \text{Obaseline value} + \text{error},$$

where  $\beta_1$  -  $\beta_6$  are parameters of fixed effects and  $\beta_0$  an intercept. The estimated treatment differences between MC2-25 cream and MC2-25 vehicle, will be reported together with the associated standard error, the 95% confidence interval, and a p-value of a test on the respective contrast corresponding to the hypothesis of no difference between treatments (superiority) (Section 5.2).

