9.2 Sample size determination

Sixty two (62) patients will be screened. 33 patients will be randomised in a 1:1 ratio of MC2-25 cream to MC2-25 vehicle. For a two-sided test with a 5% level of significance and an effect size of 1 standard deviation, this sample size will provide adequate power ($\geq 78\%$) to compare mean change in mean weekly WI-NRS from Baseline to Week 12 between MC2-25 cream and MC2-25 vehicle with 16 to 17 patients per treatment group.

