9.4.2.1 Analysis of the primary efficacy endpoint

The primary endpoint, mean change in weekly mean WI-NRS from baseline to Week 12 for MC2-25 cream compared to MC2-25 vehicle, will be analysed by a mixed model of repeated measures (MMRM) including all post-baseline assessments. The model will include the fixed effects of treatment, visit, treatment-by-visit interaction, menopausal status at baseline, ICIQ-UI-SF score at baseline, and weekly mean WI-NRS at baseline. The mean change in WI-NRS at Week 12, as well as the treatment difference will be estimated using LS-means and reported together with the associated standard error, 95% confidence intervals and p-values based on F-statistics.

On the FAS, for the primary analysis assuming missingness at random, missing data will be imputed 20 times and summarised following Rubin's rule. Following a treatment policy approach, all data will be considered.

Applying the same statistical model, in sensitivity analyses MMRM will be applied to observed cases on the FAS, MFAS and PPS, respectively, without imputation. In a while-on-treatment approach, in another sensitivity analysis on the FAS, only data up to the week of treatment

discontinuation will be considered. As detailed in the SAP, further sensitivity analyses may consider assumption of missingness not at random and other potential intercurrent events.

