#### Multiple Imputation

Post-baseline missing or invalid data will be multiply imputed within treatment groups in two steps [10]. At first, any potential intermediate missing data will be imputed 20 times using a Markov Chain Monte Carlo (MCMC) method to obtain a monotone missing data pattern. In a second step, imputation is done using a monotone regression method, fitting an analysis of covariance (ANCOVA) model stepwise visit by visit. The ANCOVA model adjusts for the effects of menopausal status at baseline, ICIQ-UI-SF score at baseline as factors, and the baseline value of the respective endpoint as a covariate. For each treatment group and each copy of the dataset, the estimated parameters and their variances are used to impute the endpoint. Starting with Week 1, the procedure is repeated on Week 4, Week 8 and Week 12, adding the possibly imputed values of the previous visits as covariates. On MI, missing score data is handled like missing continuous data.

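### The MMRM gives baseline one slope for all visits; if correlation with baseline fades, the Week 12 estimate keeps part of any chance baseline imbalance, which a baseline-by-visit term would remove cheaply

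*SAP*

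**What the plan says.** SAP 5.4.3 models each continuous endpoint with treatment, visit and their interaction as factors, and "menopausal status at baseline, ICIQ-UI-SF score at baseline, and the baseline value of the respective endpoint as covariates". Its equation gives the baseline value one coefficient, beta6, shared by every post-baseline visit. Protocol 9.4.2.1 ends its list of model terms with "treatment-by-visit interaction, menopausal status at baseline, ICIQ-UI-SF score at baseline, and weekly mean WI-NRS at baseline". Neither document has a baseline-by-visit term, and neither names the covariance structure.

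For the diary scores the modelled visits are Weeks 1, 4, 8 and 12. Under SAP 5.2, estimates at visits other than Week 12 are exploratory, so the superiority claim depends on one contrast.

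The imputation step in SAP 4.7.2 works by "fitting an analysis of covariance (ANCOVA) model stepwise visit by visit", with the baseline value as a covariate. There the baseline slope may differ from visit to visit. Under SAP 5.5, each completed dataset is then analysed with the common-slope model.

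Protocol 9.2 states that "33 patients will be randomised in a 1:1 ratio of MC2-25 cream to MC2-25 vehicle". Protocol 6.3 describes no stratification.

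**The concern.** The treatment effect may vary by visit, but the effect of baseline may not. The baseline score averages the week before treatment, and the Week 1 score averages the week directly after it. The Week 12 score lies about three months later. Entry also requires a baseline average of at least 4. It is reasonable to expect baseline to predict Week 1 better than Week 12, although the documents do not show this.

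If so, one slope cannot suit both visits, and the fit favours the visit with the least residual variance. The Week 12 comparison is then adjusted with a slope that belongs mainly to Week 1. In an unstratified trial of 33 patients some baseline imbalance is likely, and removing its effect is the purpose of the covariate. At stake is how complete that adjustment is in the one trial that will be reported, and some precision.

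**Working it through.** **Inputs from the documents.** Protocol 9.2: "For a two-sided test with a 5% level of significance and an effect size of 1 standard deviation", "with 16 to 17 patients per treatment group". Visits and model terms are as in SAP 5.4.3.

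**Assumed, because the documents give no figure.** Baseline SD 1.5 points; the correlation and SD patterns in the table; unstructured covariance; complete data; the other two covariates omitted.

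**Step 1: the plan's own figure.** A two-sample t-test (noncentral t, effect 1 SD) gives power of 78.1% with 16/16 patients and 79.4% with 16/17. The stated figure of at least 78% reproduces.

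**Step 2: size of a chance imbalance.** One SD of the difference in baseline means is 1.5 × √(1/16 + 1/17) = 0.52 points.

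**Step 3: what the common slope estimates.** Let β be the vector of visit slopes on baseline and S the residual covariance. In large samples generalised least squares gives b = w′β, with w = S⁻¹1 / (1′S⁻¹1). The Week 12 estimate is then off by (β₁₂ − b) × imbalance. Its variance is multiplied by 1 + (β₁₂ − b)² × Var(baseline) / (Week 12 residual variance).

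Taking change as the outcome subtracts 1 from every slope and leaves β₁₂ − b unchanged.

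**Worked example.** In units of the baseline SD, let the correlations with baseline be 0.8, 0.6, 0.5 and 0.4, with equal SDs and between-visit correlations of 0.7, 0.6 and 0.5 at lags 1 to 3.

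- Residual variances are 0.36, 0.64, 0.75 and 0.84.
- Weights are 0.67, 0.13, 0.08 and 0.12, so b = 0.70.
- The gap is 0.40 − 0.70 = −0.30 points per point of imbalance.
- A 0.52-point imbalance shifts the estimate by about 0.16 points. An unadjusted change score would shift by (1 − 0.40) × 0.52 = 0.31, so half is kept.
- The variance factor is 1 + 0.30²/0.84 = 1.11.

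**Step 4: other patterns.** Rising SDs are 1.7, 2.0, 2.3 and 2.5 points. Power is for an effect of 1 Week 12 residual SD; visit-specific slopes give 79.4% in large samples.

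| Correlation with baseline, Weeks 1/4/8/12 | Week 1 weight | b | β₁₂ | Gap | Variance factor | Power |
|---|---|---|---|---|---|---|
| 0.8/0.6/0.5/0.4, equal SDs | 0.67 | 0.70 | 0.40 | −0.30 | 1.11 | 75.2% |
| same, rising SDs | 0.85 | 0.89 | 0.67 | −0.22 | 1.02 | 78.6% |
| 0.8/0.5/0.3/0.2, equal SDs | 0.91 | 0.78 | 0.20 | −0.58 | 1.36 | 66.6% |
| compound symmetry 0.5, equal SDs | 0.25 | 0.50 | 0.50 | 0 | 1.00 | 79.4% |
| compound symmetry 0.5, rising SDs | 0.48 | 0.65 | 0.83 | +0.18 | 1.02 | 78.8% |

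**Step 5: simulation, 33 patients.** This includes the cost of estimating the extra slopes. Variance ratios, common slope over visit-specific, follow from the simulated SDs:

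- First row: (0.510/0.488)² = 1.09; power 73.8% against 77.6%.
- Steep row: (0.592/0.516)² = 1.32; power 65.8% against 78.8%.
- Fading with rising SDs: (0.807/0.808)² = 1.00.
- Compound symmetry, equal SDs: (0.464/0.467)² = 0.99.

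Over eleven patterns, average bias was 0.02 points or less and type I error 4.6-5.6%. With visit-specific slopes, dependence on the imbalance was −0.02 to +0.04 points per point.

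A separate set of simulations restricted baseline to 4-10 with SD 2 and fading correlations. The common slope left 0.17-0.49 points per point of imbalance and cost 0-4 points of power.

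**Step 6: against the protocol's own effect.** For an effect of 1 SD of the change score, the unadjusted test has 79.4% power, the common-slope model 79-92% and visit-specific slopes 80-95%.

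**The case against.** A main-effect baseline covariate is a valid, pre-specified MMRM, stated consistently in both documents, in a phase 2 trial whose aim is to explore efficacy. Four points stand.

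- **The mechanism is assumed.** A reader might infer that the common slope is mostly a Week 1 slope. Nothing in the documents establishes that. The weights depend on SDs, correlations and a covariance structure that are not given. Under compound symmetry with equal SDs, Week 1 has a quarter of the weight and nothing is lost; with rising SDs the shift goes the other way.
- **The estimator is not biased in the usual sense.** A reader might infer a biased primary result. Over randomisations there is no bias and the test keeps its level. The shift exists only given the imbalance that occurs. At 1 SD of imbalance it was 0.11-0.31 points in the fading patterns; with an outcome SD of 2 points the unadjusted standard error is about 2 × √(1/16 + 1/17) = 0.70.
- **The power claim is not undermined.** A reader might infer that the trial falls short of its stated power. The loss is relative to a better model, not to the plan's calculation, which is unadjusted and reproduces.
- **The imputation mismatch is not an error.** Imputing with a richer model than the analysis model is acceptable. The fix would not align the two fully either, because imputation is within arm and also lets the effects of menopausal status and ICIQ-UI-SF vary by visit.

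The calculations also leave out multiple imputation, so the sizes are indicative. None of this removes the restriction, or the fact that lifting it costs little.

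**Conclusion.** The restriction is in both documents, and it bears on the one contrast that decides superiority. Its consequence is conditional and modest. If correlation with baseline fades and the covariance is unstructured, the Week 12 estimate keeps roughly 0 to 0.55 points per point of baseline imbalance (0.58 in the steepest pattern tabulated). A 1-SD imbalance is about 0.5 points, assuming a baseline SD of 1.5.

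Relative to visit-specific slopes, the Week 12 variance is usually between about 2% smaller and 12% larger. It is about 20-35% larger only if the correlation falls steeply at constant SD, and unaffected under compound symmetry with equal SDs.

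The documents do not support calling the primary analysis biased, invalid or underpowered. This is a worthwhile, inexpensive improvement and not the correction of an error.

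**What to change.** In SAP 5.4.3, add a baseline-value-by-visit interaction to the MMRM for WI-NRS, WP-NRS and the Skindex-29 domains, in both the text and the formula. Record the addition in SAP 5.6 as a change from protocol 9.4.2.1, before unblinding. Keep menopausal status and ICIQ-UI-SF score as main effects, to limit the parameters spent in 33 patients.

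The cost is one parameter per additional visit: three for the diary scores (four visits) and two for Skindex-29 (Weeks 4, 8 and 12). If the slopes are in fact equal, or the SDs rise after baseline, up to about 2% in variance is lost. The endpoint, estimand, analysis set and data collection are unchanged.

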## 5.5 Application of Methods

The following subsections describe the application of methods per endpoint, summarized in Section 5.5.5.

### Multiple Imputation Procedure

Applicable to all primary and secondary endpoints with MI, the procedural steps are as follows. On 20 multiple complete imputed datasets as produced according to the instructions in Section 4.7.2, each dataset will be analyzed the same way. After pooling the estimates and standard errors, results will be aggregated following Rubin's rule to yield one estimate and associated standard error, and to calculate the 95% confidence interval for the treatment difference or odds ratio between treatments, respectively [11]. In data listings, multiply imputed values are described by mean values.

### 5.5.1 Primary Endpoint

The primary endpoint is the mean change in weekly mean Worst Itch Numeric Rating Score (WI-NRS) recorded in the patient's diary from Baseline to Week 12.

#### Primary Analysis

The analysis is for superiority of MC2-25 cream versus MC2-25 vehicle using the treatment policy strategy on the FAS using MI to impute missing data. The estimated treatment difference will be reported together with the associated standard error, the 95% confidence interval, and the respective p-value of testing hypotheses  $H_0$ .

#### Sensitivity Analyses

Four sensitivity analyses are planned on the primary endpoint:

- a) following the treatment policy strategy on the FAS without imputation
- b) following the treatment policy strategy on the MFAS without imputation
- c) following the treatment policy strategy on the PPS without imputation
- d) following the while on treatment strategy on the FAS without imputation

Details are given in Sections 5.2, 5.3, and 4.7.2.

### 5.5.2 Secondary Endpoints

The secondary endpoints follow two quite different analysis strategies.

The two continuous endpoints (all defined from Baseline to Week 12):

- Mean change in weekly mean Worst Pain Numeric Rating Score (WP-NRS) recorded in the patient's diary (Weekly mean WP-NRS is calculated as the average of WP-NRS values recorded in the patient's diary for 7 days prior to the in-clinic visits.)
- Change in Skindex-29 domains

will be analysed in an identical fashion to the primary endpoint described in Section 5.5.1, which includes one analysis on the FAS with imputation, and a further four sensitivity analyses, all without imputation.

The four binary endpoints (all defined from Baseline to Week 12):

- Percentage of patients obtaining a  $\geq 4$ -point improvement in weekly mean WI-NRS recorded in the patient's diary
- Percentage of patients obtaining a  $\geq 4$ -point improvement in weekly mean WP-NRS recorded in the patient's diary
- Percentage of patients obtaining a  $\geq 3$ -point improvement in weekly mean WI-NRS recorded in the patient's diary
- Percentage of patients obtaining a  $\geq 3$ -point improvement in weekly mean WP-NRS recorded in the patient's diary

will be analysed using the treatment policy strategy on the FAS in a logistic regression model with a factor for treatment, and covariates menopausal status at baseline, ICIQ-UI-SF score at baseline, as well as the baseline value of the scale the binary endpoint is derived from (WI-NRS or WP-NRS). The estimated log odds ratios between treatments at Week 12 will be reported, along with the 95% confidence interval. The logistic regression models will be carried out on worst case imputation data, where missing endpoint data is assumed to be no response.

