9.4 Statistical analyses

9.4.1 General approach

The methodology presented below represents a brief overview of the statistical methods that will be fully detailed in the statistical analysis plan (SAP). The SAP will be finalised before the database is locked. Any changes to the methods described in the final SAP will be described and justified in the clinical trial report. All statistical analyses will be performed using SAS statistical software (Version 9.4 or higher).

Statistical significance will be tested at the two-sided 5% significance level unless otherwise specified. Superiority is concluded if a p-value of statistical hypothesis testing is below the significance level and the estimate of treatment difference is in favourable direction for MC2-25 cream. Estimates of treatment effects and differences at timepoints other than Week 12 will be reported exploratively.

Categorical variables will be described by summary tables of frequencies (counts and percentages) per treatment group, continuous parameters by displaying arithmetic mean, median, minimum and maximum values, standard deviation, and, where applicable, interquartile ranges.

All collected and derived data will be presented in individual patient data listings.

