9.4.2.2 Analysis of the secondary endpoints

Secondary endpoints include mean changes in weekly mean WP-NRS and in Skindex-29 domain scores as well as percentages of participants obtaining a ≥ 3 -point or a ≥ 4 -point improvement in weekly mean WI-NRS and weekly mean WP-NRS, respectively.

Mean changes in weekly mean WP-NRS and in Skindex-29 domain scores on the FAS will be analysed as described in Section 9.4.2.1 for primary and sensitivity analyses on mean changes in weekly mean WI-NRS. On the FAS, percentages of participants obtaining a ≥ 3 -point or a ≥ 4 -point improvement in weekly mean WI-NRS and weekly mean WP-NRS will be analysed by means of logistic regression adjusting for respective NRS scores at baseline. If the endpoint is missing, no improvement is assumed.

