### 4.3 Subgroups and Confounding Factors for Analysis

The mixed model for repeated measures (MMRM) for continuous endpoints (primary and secondary) will be adjusted by menopausal status at baseline, ICIQ-UI-SF score at baseline, and the respective baseline

value of the endpoint being modelled. Similarly for the two binary secondary endpoints, which will be analyzed using a logistic regression at Week 12, the models will be adjusted by menopausal status at baseline, ICIQ-UI-SF score at baseline, and the baseline value for each scale the binary endpoint is derived from (WI-NRS or WP-NRS).

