### 5.4.1 Binary Data

The binary secondary endpoints (Section 2.4.1) will be analysed using a logistic model with effects of treatment, menopausal status at baseline, ICIQ-UI-SF score at baseline, and the baseline value for each scale the binary endpoint is derived from (WI-NRS or WP-NRS) as factors. The estimated log odds ratios between the treatments at Week 12 will be derived together with the associated standard error and 95% confidence intervals. These binary endpoints will be summarized in descriptive tables and visualized in bar charts, in both cases stratified by treatment group and visit.

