### 5.6 Changes and Clarifications to Analyses Planned in the Study Protocol

There are two changes to the sub-group analyses specified in section 9.4.6 in the protocol:

- The stratification by country will not be carried out as the study is carried in only one country
- Similarly, the stratification by site is deemed superfluous due to both the smaller sample size than expected, and possibly sites with very small sample sizes

In section 9.4.8 the exploratory endpoint burden living with VLS is only assessed at Screening and will only be listed, not described in summary tables.

Statistical within-treatment group pre-post testing was added to descriptive summary tables of selected endpoint as specified above.

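### The SAP adds menopausal status and ICIQ-UI-SF score to the protocol's responder model without declaring it, at a modest cost in precision and with no visible gain; the cost is large only if ICIQ-UI-SF is coded as a class factor.

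*SAP*

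**What the plan says.** Protocol 9.4.2.2 states that the responder percentages "will be analysed by means of logistic regression adjusting for respective NRS scores at baseline". The protocol names menopausal status and ICIQ-UI-SF score as model terms only for the MMRM (9.4.2.1).

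SAP 5.5.2 gives the logistic model a treatment factor and "covariates menopausal status at baseline, ICIQ-UI-SF score at baseline, as well as the baseline value of the scale the binary endpoint is derived from". SAP 4.3 and 5.4.1 add the same two terms, but the three sections do not agree in detail:

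- SAP 5.4.1 ends its list of model effects with "WI-NRS or WP-NRS) as factors", where 5.5.2 calls the same terms covariates.
- SAP 4.3 opens with "Similarly for the two binary secondary endpoints, which will be analyzed using a logistic regression at Week 12", where 5.5.2 lists four.

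SAP 5.6, the section for changes and clarifications, begins "There are two changes to the sub-group analyses specified in section 9.4.6 in the protocol". It then covers the patient-journey listing and the added within-group tests. It says nothing about the responder covariates. Neither document names a method for a logistic fit that does not converge or separates.

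**The concern.** SAP 2.4.1 classes these endpoints with the primary as confirmatory. A reader who relies on SAP 5.6 to learn what changed would not know that four secondary analyses use a different model from the protocol's.

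The statistical worry is sparse data. The protocol model has two slopes (treatment, baseline NRS). The SAP model has four if ICIQ-UI-SF is linear. With, say, 7 to 14 responders, that takes responders per slope from 3.5–7 down to 1.75–3.5. In a maximum-likelihood logistic fit this can widen the interval for the treatment log odds ratio, cost power, and more often leave some coefficient without a finite estimate.

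**Working it through.** **1. The plan's own figure.** Protocol 9.2 says: "33 patients will be randomised in a 1:1 ratio of MC2-25 cream to MC2-25 vehicle". Its power statement starts "For a two-sided test with a 5% level of significance and an effect size of 1 standard deviation" and claims at least 78%. For a two-sample t-test the noncentrality is d × √(n₁n₂/(n₁+n₂)).

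- 16/16: √8 = 2.83 on 30 df, power 78.1%.
- 16/17: √(272/33) = 2.87 on 31 df, power 79.4%.

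The figure reproduces. It concerns the primary endpoint only. Neither document gives a responder rate or power for the four responder endpoints, so the rest needs assumptions.

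**2. Main simulation.** From the documents: 33 patients split 16/17, a true effect of 1 SD, missing counted as non-response, 63% incontinent (Protocol 4.2.4), ICIQ-UI-SF range 0–21, WI-NRS entry floor of 4. Assumed: SD 2, vehicle mean improvement 0.5 or 1.5 points, 10% missing, 60% or 80% menopausal, baseline WI uniform 4–9.5 and WP uniform 0–9, added covariates either null or prognostic. This gave 24 scenarios of 600 trials. Expected responders run from 17×0.02 + 16×0.11 = 2.1 to 17×0.23 + 16×0.53 = 12.4. Separation was found by linear programming, once for any coefficient and once for the treatment coefficient.

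Protocol model against SAP model, ICIQ-UI-SF linear:

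- Median SE of the treatment log odds ratio, where both models fit: 6% to 17% larger.
- Wald significance, failed fits counted as failures: between +0.5 and −4.0 points in 18 scenarios, and −4.6 to −7.8 in the other six (for example 48% to 44%, 25% to 20%, 22% to 15%).
- Separation of any coefficient: 1–75% of trials against 4–94%, a ratio of 1.1 to about 21.
- Treatment log odds ratio non-finite: 1–75% against 1–78%, an increase of 0.3 to 3.0 points.

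**3. Four example settings.** 1,000 trials each; vehicle improvement 1.5, 80% menopausal, null covariates.

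| Endpoint (approximate rates, vehicle/cream) | Any separation, protocol → SAP | Treatment OR non-finite, protocol → SAP linear | Treatment OR non-finite, ICIQ-UI-SF as class |
|---|---|---|---|
| WI ≥3 (20%/54%) | 2.4% → 11.0% | 2.4% → 3.2% | 22.4% |
| WI ≥4 (10%/37%) | 17.0% → 33.8% | 17.0% → 18.2% | 47.8% |
| WP ≥3 (13%/36%) | 8.7% → 26.4% | 8.7% → 9.4% | 39.4% |
| WP ≥4 (5%/21%) | 41.0% → 64.9% | 41.0% → 43.8% | 73.2% |

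As a class variable ICIQ-UI-SF has about 13 observed levels, and some coefficient separates in every trial.

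**4. Why columns two and three differ.** Suppose 20% are pre-menopausal and 20% respond, independently. The chance that no pre-menopausal woman responds is (1 − 0.2×0.2)³³ = 0.96³³ = 26%. The menopausal coefficient then diverges, but the treatment odds ratio usually stays finite.

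**5. Stronger covariates.** A second simulation (16/17 patients, about 7–14 responders, covariates null to strongly prognostic) gave an SE 7–31% larger and 0.5–4 points less power under the SAP model in every scenario with a true effect. A third, with ICIQ-UI-SF prognostic and 5,000 trials, put the two models within a point of each other (54.7% and 54.0%).

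**The case against.** The protocol calls its methods a "brief overview of the statistical methods that will be fully detailed in the statistical analysis plan (SAP", so the SAP may add detail. Protocol 4.2.4 says incontinence is recorded so that the analysis can account for it, and both covariates are already in the primary MMRM. Using the same set in the responder models is a defensible choice, stated in three SAP sections. The power cost is mostly a few points and rests on assumed rates. The literal class reading of 5.4.1 would also make the baseline weekly mean a class variable, which can hardly be meant.

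Much of this stands. It does not explain the omission from 5.6: the protocol states one covariate set and the SAP uses another. Nor can the class reading be set aside as an isolated slip, since SAP 4.7.2 also calls ICIQ-UI-SF a factor in the imputation model.

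A reader might infer from the any-separation column that the added covariates multiply failures of the reported result. They do not. The SAP reports the treatment log odds ratio, which fails at most about 3 points more often with ICIQ-UI-SF linear. A reader might also infer that the protocol model would cure separation. It would not: at WP ≥4 the treatment odds ratio is already non-finite in 41.0% of the example trials, because responders are few.

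**Conclusion.** The departure is real and undeclared. With ICIQ-UI-SF linear, its cost is modest:

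- The treatment SE rises by roughly 6–17% with null or modestly prognostic covariates. It rises by up to about 30% with strongly prognostic ones, where SE alone overstates the loss because the conditional odds ratio also moves away from 1.
- Power generally falls by 0 to 4 points, and by up to 8 in some assumed scenarios. No setting showed a material gain.
- Some coefficient separates more often, frequently severalfold, but mostly the one for menopausal status. A non-finite treatment odds ratio rises by about 0.3–3 points.

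The harm becomes large only under class coding of ICIQ-UI-SF: in the four example settings the treatment odds ratio is non-finite in 22–73% of trials, against 2–41% under the protocol model. The SAP's wording leaves this open.

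All these sizes depend on assumed responder rates, menopausal share and covariate effects. The mismatch between the documents does not. Nothing here touches the primary analysis, and the documents give no sign that the covariates were chosen with knowledge of results.

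**What to change.** 1. In SAP 4.3, 5.4.1 and 5.5.2, specify treatment plus the respective baseline NRS as a continuous term for all four responder endpoints, and correct the count of two in 4.3.
2. Move the model with menopausal status and ICIQ-UI-SF, the latter stated as one linear term, to a labelled sensitivity analysis, and list it in SAP 5.6.
3. Fit the responder models by Firth penalised (or exact) logistic regression, named in advance, since restoring the protocol covariates alone leaves most treatment-effect separation in place.

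The cost is SAP wording and a small programming change. The drawback is that the responder models would no longer share the MMRM's covariates; the sensitivity analysis keeps that comparison available.
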